11.7 Accountability procedures

Local pharmacy personnel will be responsible for ensuring that the IMP is managed and dispensed to participants in accordance with the duly approved current protocol.

Accountability logs for AZD8895 and AZD1061 are included in the Pharmacy Pack provided by CTR upon site activation.

Trial specific accountability is not required for vaccines.

The investigator is responsible for keeping accurate records of the clinical supplies received from AstraZeneca or designee, of the amount dispensed to and returned by the participants and the amount remaining at the conclusion of the trial.

Upon completion or termination of the trial, all unused and/or partially used investigational product will be destroyed at the site per institutional policy after authorisation from CTR. It is the Investigator's responsibility to arrange for disposal of all empty containers, provided that procedures for proper disposal have been established according to applicable federal, state, local and institutional guidelines and procedures, and provided that appropriate records of disposal are kept.

12 Sample Management

Sites will be provided with a translational sample collection kit. Up to 50ml of blood will be collected from participants at the following timepoints:

- Baseline (Predose)
- 28, 56, 112 and 180 days post AZD7442

Samples will be processed and frozen onsite. The CTR will arrange regular batch collections of samples on dry ice to the relevant Laboratory. Samples may be stored by laboratories approved by the Sponsor.

A subset of sites will be asked to provide fresh samples for additional analysis. Full details on sample collection and management can be found in the Laboratory Manual.

Lateral flow tests for SARS-CoV-2 infection will be performed for a subset of participants routinely on day 0, 28, 56, 112 and 180. If the lateral flow test is positive for SARS-CoV-2 infection, a nasal PCR swab will be taken to be sent for testing.

All participants testing positive to SARS-CoV-2 throughout the trial will also be asked to send a nasal PCR swab for testing.

12.1 Analysis

Immunogenicity will be assessed by a variety of immunological assays at University of Oxford research laboratories or at designated specialist laboratories. This will include:

- Quantify antibody responses to SARS-CoV-2 Spike and non-Spike antigens
- Assessment of T-cell responses using ex vivo ELISpot assays for interferon gamma and flow cytometry assays or other relevant assays of cellular function and phenotype.
- Assessment of neutralising antibody against live and/or pseudotype SARS-CoV-2 virus variants
- B cell analyses, and Peripheral blood mononuclear cell (PBMC) analysis.

Serology and PK analysis will be conducted at research laboratories as specified in the Laboratory Manual according to laboratories SOPs.

A subset of participants will be regularly tested for SARS-CoV-2 infection. All samples positive for SARS-CoV2 infection will be sequenced to identify escape variants.

DNA analysis of genetic polymorphisms potentially relevant to vaccine immunogenicity and/or SARS-CoV-2 pathogenesis or SARS-CoV-2 therapeutics and gene expression studies amongst others may be performed at the discretion of the Investigators.

This is not an all-inclusive list: additional assays will be performed as more information becomes available about the immune response elicited during the trial.

Should a participant have a SARS-CoV-2 infection, severity should be assessed using the WHO Clinical Progression Scale (see Appendix 2).

12.1.1 Biobanking

NRDIF

Participants will be informed that there may be leftover samples of their blood (after all testing for this trial is completed), and that such samples may be stored indefinitely for possible future research (exploratory immunology) will be able to decide if they will permit such future use of any leftover samples. With the volunteers' informed consent, any leftover cells and serum/plasma will be frozen indefinitely for future analysis of SARS-CoV-2 and other coronaviruses related diseases or vaccine-related responses. If a subject elects not to permit this, all of that subject's leftover samples will be discarded after the required period of storage to meet Good Clinical Practice (GCP) and regulatory requirements. Samples that are to be stored for future research will be transferred to the Oxford Vaccine Centre (OVC) Biobank (REC 16/SC/0141) or equivalent Human Tissue Authority (HTA) licenced biobank.

13 Trial procedures

Appointments that do not require clinical intervention can be taken by phone where possible to limit participant's exposure. This may include questionnaires that can be emailed or posted where this remains in the best interest of the participant. The participant should be approached by the treating team to ensure that they are happy to be contacted in this way.

Table 6 summarizes the trial procedures to be performed at each visit by the PI or qualified designee. Individual trial procedures are described in detail below. It may be necessary to perform these procedures at unscheduled time points, if deemed clinically necessary by the investigator.

Where possible, participants' visits should be aligned with their routine visits.

13.1 Assessments

Baseline Assessments

All baseline assessments should be performed after consent has been obtained and within 28 days of treatment. Participants will be required to attend clinic for blood sample collection and treatment. The following assessments will need to be done:

- Completion of eligibility checklist form
- Participant informed consent
- Full Medical History
- Randomisation as per Section 9.5 of the protocol
- Participants should be asked about their previous SARS-CoV-2 vaccination history. The information should be collected on the SARS-CoV-2 vaccine form.
- Prior and Concomitant Medications Review of any medications received within 28 days before the first dose of trial treatment
- Participant behavioural questionnaires (risk behaviour changes, PROMIS 10, EQ-5D-5L)

AZD7442 treatment (this can be done on the same day as baseline assessments)

Day 0

- A negative urine dipstick pregnancy test should be performed to confirm eligibility for women of child-bearing potential.
- Toxicity assessment (CTCAE 5.0)
- Blood sample collection and completion of the sample eCRF
- Safety bloods (full blood count (FBC), Urea and electrolytes (U&E), Liver function test (LFT) and bone profile)
- Full Physical Examination including vital signs, weight and height
- Blood sample collection prior to AZD7442 dosing and completion of the sample eCRF
- Routine (asymptomatic) lateral flow testing for SARS-CoV-2 infection (only subset of participants). If the lateral flow test is positive for SARS-CoV-2 infection, a nasal PCR swab should be taken to be sent for testing.

NB: The assessments above should be performed *before* the administration of AZD7442.

• Dosing with AZD7442

On Day 14 post AZD7442 (+/- 3 days):

• Toxicity assessment via telephone consultation with patient to check on symptoms.

On Day 28 post AZD7442 (+/- 3 days):

- Clinical review
- Vital signs
- Blood sample collection and completion of the sample eCRF
- Safety blood samples (FBC, U&E, LFT and bone profile)
- Concomitant Medications Review
- Toxicity assessment (CTCAE 5.0)
- Routine (asymptomatic) lateral flow testing for SARS-CoV-2 infection (only subset of participants). If the lateral flow test is positive for SARS-CoV-2 infection, a nasal PCR swab should be taken to be sent for testing.

NB: The assessments above should be performed *before* the administration of SARS-CoV-2 vaccine booster.

• SARS-CoV2 vaccine booster administration as per randomisation allocation. This should be given 28 days (+/- 3 days) post AZD7442.

Follow-up Assessments (+/- 3 days for day 56 assessment and +/- 7 days for day 112 and 180, assessments):

The follow up assessments at Day 56, 112 and 180 (post AZD7442) include:

- Clinical review (Day 56,)
- Vital signs (Day 56)
- Concomitant Medications Review (Day 56, 112 and 180)
- Toxicity assessment (Day 56)
- Blood samples collection (Day 56, 112 and 180)
- Safety blood samples (FBC, U&E, LFT and bone profile) (day 56 and 180)
- Routine (asymptomatic) lateral flow testing for SARS-CoV-2 infection (day 56, 112 and 180) (only subset of participants). If the lateral flow test is positive for SARS-CoV-2 infection, a nasal PCR swab should be taken to be sent for testing.
- Participant behavioural questionnaires (risk behaviour changes, PROMIS 10, EQ-5D-5L) (day 112 and 180)

13.1.1 Reduction of follow up period

The Food and Drug Administration (FDA) released an announcement at the end of January 2023 advising that the use of Evusheld should be limited to when the combined frequency of non-susceptible SARS-CoV-2 variants nationally is less than or equal to 90 %. The non-susceptible SARS-CoV-2 variants included the XBB, CH.1.1 and BQ.1 sub-lineages of the Omicron variant. At this time in the U.S., fewer than 10 % of circulating variants were susceptible to Evusheld, so the FDA removed the use of Evusheld until further notice in the U.S. The link below provides further information regarding this announcement: https://www.fda.gov/drugs/drug-safety-and-availability/fda-announces-evusheld-not-currently-authorized-emergency-use-us

At this time the UK had not yet reached a threshold where \geq 90 % of the circulating variants were Evusheld-resistant SARS-CoV-2 variants so the decision was made to continue the trial as planned but closely monitor the data published weekly by the Office for National Statistics (ONS).

After monitoring the data on the UK SARS-CoV-2 infection survey that was published by the ONS over the following months, the decision was made to pause recruitment within the RAPID-PROTECTION study at the beginning of April 2023, since the percentage of circulating Evusheld resistant SARS-CoV-2 variants had exceeded the 90 % threshold. The decision was also made to reduce the follow-up period from 12 months to 6 months for all patients.

A Changes to Follow up Notification form has been created to notify existing participants of these changes and this should be provided to all participants as soon as possible.

13.2 Not permitted during the study

Additional vaccines may affect the results of the study and not give an accurate picture of the protection provided by Evusheld. Unless the study team specifically advise otherwise, participants are not permitted to receive any of the approved NHS SARS-CoV-2 vaccinations for 3 months after their SARS-CoV-2 vaccination within the study.

13.3 Ad hoc assessments

Cases of confirmed SARS-CoV-2 should be documented within the CRF. Should a participant have a COVID-19 infection, COVID-19 severity should be assessed using the WHO Clinical Progression Scale (see Appendix 2). Participants testing positive should be reminded to take and send a nasal PCR swab sample for sequencing analysis to monitor for escape variants.

Table 6. Schedule of enrolment, interventions and assessments

Procedures				Visits			
	Baseline† Treatment Phase				Follow Up		
		Day 0	Day 14	Day 28	Day 56	Day 112	Day 180
Informed consent	x						
Medical history	x						
Clinical review				x	x		
Inclusion/Exclusion criteria	x						
Physical examination		x					
Vital signs (including height and weight)		x		x	x		
Concomitant Medications Review	x			x	x	x	x
Toxicity assessment		x	x***	x	x		
Urine pregnancy test	x						
Blood sample collection		X*		x	x	x	x
Safety blood sample (FBC, LFT, bone profile and U&E)		x*		x	x		x
AZD7442 administration		x					

Oxford University Hospitals NHS Foundation Trust

SARS-CoV-2 vaccine administration				x			
Routine (asymptomatic) lateral flow testing for SARS- CoV-2 infection**		x		x	x	x	×
COVID-19 infection severity (where applicable)			x	x	x	x	x
Participant questionnaires (risk behaviour changes, PROMIS 10, EQ-5D-5L)	x					x	x

⁺ Within 28 days prior to AZD7442 administration

* Sample collected prior to AZD7442

** Lateral flow testing for SARS-CoV-2 infection to be performed for a sub-set of participants. If the lateral flow test is positive for SARS-CoV-2 infection, a nasal PCR swab will be taken to be sent for testing.

*** Toxicity assessment can be done via telephone call with the participant

14 Pharmacovigilance

The Principal Investigator is responsible for ensuring that all site staff involved in this trial are familiar with the content of this section.

All SAEs must be reported immediately (and within 24 hours of knowledge of the event) by the PI at the participating site to the CTR PV and Safety Specialist unless the SAE is specified as not requiring immediate reporting (see section 14.2). This includes SAEs related to IMPs.

14.1 Definitions

Table 7: definitions of pharmacovigilance terms

Term	Definition				
Adverse Event (AE)	Any untoward medical occurrence in a participant or clinical trial participant administered a medicinal product and which are not necessarily caused by or related to that product				
Adverse Reaction (AR)	Any untoward and unintended response in a clinical trial participant to an investigational medicinal product which is related to any dose administered to that participant				
Serious Adverse Event (SAE)	 Any adverse event that – 1. Results in death 2. Is life-threatening* 3. Required hospitalisation or prolongation of existing hospitalisation** 4. Results in persistent or significant disability or incapacity 5. Consists of a congenital anomaly or birth defect 6. Other medically important condition*** 				
Serious Adverse Reactions (SARs)	Any SAE occurring in a clinical trial participant for which there is a reasonable possibility that it is related to the IMP at any dose administered.				
Suspected Unexpected Serious Adverse Reactions (SUSARs)	A SAR, the nature and severity of which is not consistent with the Reference Safety Information (RSI) for the IMP.				

*Note: The term 'life-threatening' in the definition of serious refers to an event in which the trial participant was at risk of death at the time of the event or it is suspected that use or continued use of the product would result in the participants death; it does not refer to an event which hypothetically might have caused death if it were more severe.

**** Note:** Hospitalisation is defined as an inpatient admission, regardless of the length of stay, even if the hospitalisation is a precautionary measure for continued observation. Pre-planned hospitalisation e.g. for pre-existing conditions which have not worsened, or elective procedures, does not constitute an SAE.

******* Note: other events that may not result in death, are not life-threatening, or do not require hospitalisation, may be considered as an SAE when, based upon appropriate medical judgement, the event may jeopardise the participant and may require medical or surgical intervention to prevent one of the outcomes listed above.

14.2 Trial Specific SAE Reporting requirements

In addition to the SAE reporting requirements defined in Table 7, for the purposes of this trial the following events will also be considered adverse events of special interests (AESI) and must be captured on the SAE form and reported to the CTR with 24 hours of knowledge of the event:

- Anaphylaxis and other serious hypersensitivity reactions including immune complex disease (defined by regulatory criteria of seriousness and MedDRA SMQ Hypersensitivity (Narrow)) – Grade 3 and above
- Cardiac events (i.e. cardiac ischemia, cardiac failure and thrombotic events)
- Injection site reactions (defined by MedDRA HLT Injection site reactions) grade 3 and above
- SARS-CoV-2 infections requiring hospitalisation, life threatening or death within start of treatment and 28 days following vaccine booster. Following the 28 days, reporting of these events are to be captured on the relevant eCRF.

For the purposes of this trial the following events will not require reporting as SAEs:

Hospitalisations for:

- Disease treatment
- Receipt of supportive care for disease treatment related toxicities (e.g. neutropenic sepsis, vomiting for cancer participants) (unless there is concern this has been exacerbated by vaccination)
- Disease progression (unless there is concern this has been exacerbated by vaccination)
- Pre-planned elective procedures (unless the condition worsens)
- Injection site reactions (defined by MedDRA HLT Injection site reactions) grade 2 and below
- Anaphylaxis and other serious hypersensitivity reactions including immune complex disease (defined by regulatory criteria of seriousness and MedDRA SMQ Hypersensitivity (Narrow)) – Grade 2 and below

Pre-existing conditions should only be reported if they meet the definitions for an SAE and if the condition worsens by at least one CTCAE grade.

Pre-existing conditions should be completed in the participant's notes and on the relevant toxicities CRF page and forwarded to the CTR in the normal timeframes for CRFs.

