6.1.2 Risk assessment of AZD7442

The two monoclonal antibodies that make up AZD7442 both target SARS-CoV-2 spike protein for neutralization of the virus and do not have a human target. As such, the risks associated with AZD7442 are akin to risks associated with the administration of any immunoglobulin with no risk associated with mechanism of action.

As with other immunoglobulins, risks include but are not limited to, anaphylaxis and other serious hypersensitivity reactions including immune complex disease. Other risks include injection site reactions, and Antibody-dependent enhancement (ADE) disease, the latter of which is a theoretical risk.

Two different syndromes exist: 1) ADE, which involves increased binding efficiency of virus-antibody complexes to Fc receptor bearing cells and which triggers virus entry. The mAbs in AZD7442 have been designed with a modification to prevent binding to cellular Fc receptors, so the risk of ADE occurring via this mechanism should range from very low to none. 2) VAERD, which is a distinct clinical syndrome that occurred in young children in the 1960s when whole inactivated virus vaccines for measles and RSV were tested. Immunizing with limiting doses of RSV antigen, especially with conformationally incorrect antigens, can result in 2 major types of immunological phenomena: a) A relatively high ratio of antibody that binds, but does not neutralize, virus could potentially result in immunogenic cell death and complement activation (leading to inflammation and airway obstruction); b) immunization with whole inactivated virus vaccines can result in allergic inflammation characterized by, e.g., increased mucus production, airway hyperresponsiveness, and attenuated cytolytic T cell activity (T helper 2 cell immune response). This mechanism, induced by vaccines, should not be provoked by mAbs.

At present, there are no identified risks nor emerging safety profiles associated with AZD7442. The potential impact of the trial drug on other medicinal products including vaccines (including any SARS-CoV-2 vaccine) is not known. There is a possibility that receiving the trial drug prior to vaccination may result in the vaccine being less effective up to 9 months to 1 year or more or may cause a vaccine to have other currently unknown side effects.

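### Section 14.2 waives SAE reporting for Grade 2 or lower hypersensitivity and injection site reactions that Table 7 would class as serious when the participant is admitted

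*Protocol*

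**What the plan says.** Section 14.1 (Table 7) sets out what makes an event serious: death, threat to life, hospitalisation, disability, congenital anomaly or other medical importance. The hospitalisation criterion reads "Required hospitalisation or prolongation of existing hospitalisation", and the note to the table explains hospitalisation as "an inpatient admission, regardless of the length of stay, even if the hospitalisation is a precautionary measure for continued observation". CTCAE grade plays no part in the definition. Section 14.5.1 asks for SAEs to be graded, so grade describes an SAE and does not decide whether an event is one.

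Section 14.2 modifies this in two directions. Serious hypersensitivity must go on the SAE form within 24 hours when it is "MedDRA SMQ Hypersensitivity (Narrow)) – Grade 3 and above". A second list then gives events for which "For the purposes of this trial the following events will not require reporting as SAEs". That list, under a sub-heading about hospitalisations, repeats the same category, "Anaphylaxis and other serious hypersensitivity reactions including immune complex disease (defined by regulatory criteria of seriousness", this time ending "MedDRA SMQ Hypersensitivity (Narrow)) – Grade 2 and below". Injection site reactions of Grade 2 or below are on the list too.

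The opening of section 14 refers to 14.2 as the place where some SAEs are excused from immediate reporting. It does not say that they are excused from SAE reporting altogether.

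Table 1 makes SAE reporting the outcome measure for the co-primary safety objective.

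**The concern.** Seriousness and severity grade are different scales, and the exemption uses one to cancel the other. The hypersensitivity item is defined by the seriousness criteria, so the events it excuses are SAEs by the protocol's own wording.

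The remaining exemptions concern the underlying illness or planned care, and most carry a safeguard. Supportive care and disease progression stay reportable if vaccination may have made matters worse, and elective procedures stay reportable if the condition worsens. The hypersensitivity and injection-site items are the two most plausibly caused by trial treatment, and neither has a safeguard. Section 6.1.2 says of AZD7442 that "risks include but are not limited to, anaphylaxis and other serious hypersensitivity reactions including immune complex disease", and goes on to name injection site reactions.

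At stake are the completeness of a co-primary outcome, the consistency of counts between sites, and a clear path for possible drug reactions into safety review.

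**Working it through.** The protocol gives no figure to reproduce here. The check sets its rules side by side.

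| Event | Table 7, section 14.1 | Section 14.2 |
|---|---|---|
| Grade 3 hypersensitivity reaction, admitted | SAE | SAE form within 24 hours |
| Grade 2 hypersensitivity reaction, admitted for observation | SAE (hospitalisation) | Not reportable as an SAE |
| Grade 2 injection site reaction, admitted for observation | SAE (hospitalisation) | Not reportable as an SAE |
| Grade 2 hypersensitivity reaction, no admission, no other criterion met | Not an SAE | No conflict |

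The second and third rows contradict each other across the two sections.

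**Does the sub-heading matter?** The text was read from a PDF, so it is uncertain which items belong under the hospitalisation sub-heading. If both do, the exempt cases are exactly the admitted ones, and admission is a Table 7 criterion. If they do not, the hypersensitivity item still covers only events meeting a seriousness criterion, because it is "defined by regulatory criteria of seriousness and MedDRA SMQ Hypersensitivity (Narrow"). The injection-site item would then cover all low-grade reactions, including admitted ones. The conflict survives either reading.

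**Can the combination occur?** Table 4 in section 11.3 recognises mild and moderate hypersensitivity reactions. A precautionary admission for one of these is enough to meet Table 7.

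**What follows downstream?**
- Section 16.1.6 presents SAEs as a listing, which depends on events being identified as SAEs.
- Section 14.3 assesses causality for each SAE and section 14.4 assesses expectedness for each SAR. Table 7 defines a SAR as a kind of SAE.
- Section 14.5.2 identifies SUSARs from investigators' reports of suspected SARs.
- Low-grade events can still be captured as AEs: after the injection (section 11.2.4), at the toxicity assessments on Days 0, 14, 28 and 56 (section 13.1), and in the AE incidence rates (section 16.1.6).

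**Size.** The protocol gives no rate for events that are both serious and Grade 2 or below. The nearest figures are from PROVENT (sections 4.5 and 4.6.1): one anaphylaxis and one immune complex disease among 3460 participants on AZD7442. Scaled to this trial, 2 / 3460 × 350 = 0.2 participants, before any restriction to serious low-grade cases. Section 6.1.2 says that the anaphylaxis was classified as non-serious. This points to a small number but is no estimate for this trial, because PROVENT used 300 mg in a different population.

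**The case against.** The best defence is that 14.2 waives only speed. The opening of section 14 speaks of immediate reporting. Section 14.5.1 ties the 24-hour form to events that need it, and separately requires serious adverse reactions to be reported until the end of follow-up. Section 14.5.2 has suspected SARs reviewed at once. A drug-related serious hypersensitivity reaction is a SAR, so it might still reach SUSAR review. This part stands: a reader might infer that exempt events bypass causality, expectedness and SUSAR review entirely, and the documents do not establish that. Even so, 14.2 speaks of not reporting the events as SAEs and offers no later SAE route, so the sections still disagree.

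A second defence is that excusing certain hospitalisations is the whole purpose of such a list. That is fair for disease treatment, progression and elective care. It does not carry over to possible reactions to the trial products that have no safeguard.

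Two stronger readings should be resisted. Hypersensitivity is the first risk named in section 6.1.2, but it is not the only one singled out: that section also names injection site reactions and a theoretical enhancement risk, and 14.2 lists four classes of special interest. Nor can the effect be sized from PROVENT's 1.4% SAE proportion (0.014 × 350 = 4.9 participants, so that one lost event would be about a fifth). That proportion comes from 300 mg in a population with few highly immunosuppressed patients, and the lost event is assumed.

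**Conclusion.** The text is wrong as written. Admitted Grade 2 or lower hypersensitivity and injection site reactions are SAEs under 14.1 and exempt under 14.2, and sections 14 and 14.2 differ on what is being waived. A site that follows Table 7 and a site that follows 14.2 would count the same event differently in a co-primary outcome.

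The loss is of the serious label and of a clear review route, not necessarily of the event from all safety data. The number affected cannot be estimated from the protocol and is probably small. The conclusion rests on the wording alone and does not depend on any assumed event rate.

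**What to change.** 1. On the Grade 2 and below hypersensitivity line of section 14.2, delete the word *serious* and the reference to regulatory seriousness criteria.
2. On both that line and the injection-site line, add: *unless any Table 7 seriousness criterion is met*. The injection-site line has no seriousness wording to remove, so the addition is enough there.
3. Reconcile the opening of section 14 with sections 14.1, 14.2 and 14.5.1, so that they say in the same terms whether 14.2 waives SAE reporting or only immediate reporting. If only immediate reporting is waived, state how and when these SAEs are reported.

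The cost is a wording amendment and a few extra SAE forms. Only reporting changes; participants' treatment is unaffected.

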4.7.1 Hypotheses to be tested

1) That treatment with AZD7442 in combination with a SARS-CoV-2 vaccine is safe and well tolerated,

2) That vaccination with a SARS-CoV-2 vaccine does not reduce AZD7442 titres in humans and

3) That AZD7442 in combination with a SARS-CoV-2 vaccine enhances immune responses to SARS-CoV-2.

5 Trial objectives/endpoints and outcome measures

We propose to test the following objectives:

Table 1: Objectives and outcome measures

	Objectives	Outcome measures
Co-Primary	To assess the pharmacokinetics of AZD7442 administered as a single dose of 600 mg IM in immunosuppressed patients	Serum samples will be taken at Day 0 (Predose AZD7442), and days 28, 112 and 180 post AZD7442 treatment and samples shipped to an AstraZeneca approved laboratory for Pharmacokinetics (PK) analysis.
		Samples collected for analyses of AZD7442 serum concentration may also be used to evaluate safety or efficacy aspects related to concerns arising during or after the trial. PK results from the trial will be compared to results from other phase III studies with AZD7442 such as PROVENT.
	To assess the safety and tolerability of a single IM dose of AZD7442, followed by SARS-CoV2 vaccine booster 28 days later with reference to serious adverse events (SAEs) in highly vulnerable patients.	SAE reporting throughout the trial using CTCAE V5.0
	To assess the SARS-CoV-2 specific humoral and cellular immune response against SARS-CoV-2 variants, when a SARS-CoV-2 vaccine is administered 28 days after AZD7442 in patients who are immune suppressed.	The function and magnitude of SARS-CoV-2 specific antibody and T cell responses will be measured at baseline and at additional multiple timepoints after the administration of AZD7442.
		Assays will quantify the amount of serum antibodies to the spike (S) and the nucleocapsid (N) antigens of SARS-CoV-2. This assay will enable the discrimination of antibody responses to SARS-CoV-2 that results from vaccination and/or SARS-CoV- 2 infection. Ab function, including viral neutralisation will be assessed.

		The magnitude and function of SARS-CoV-2 specific T cell responses following the booster vaccination will use assays that give insight into T cell function. Laboratories will measure neutralizing antibodies to SARS-CoV-2 using validated wild-type neutralization assay or pseudo- neutralization assays.

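### The Section 14.2 SAE exemptions for disease progression and treatment toxicity are lifted only for concern about vaccination, not AZD7442, and conflict with the rules on serious reactions to any IMP

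*Protocol*

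**What the plan says.** Section 5, Table 1, sets as a co-primary objective "To assess the safety and tolerability of a single IM dose of AZD7442, followed by SARS-CoV2 vaccine booster 28 days later". This objective is judged on SAEs, and its outcome measure is "SAE reporting throughout the trial using CTCAE V5.0".

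The opening of Section 14 requires all SAEs to be reported within 24 hours, "unless the SAE is specified as not requiring immediate reporting (see section 14.2). This includes SAEs related to IMPs".

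Section 14.2 then introduces a list of hospitalisations: "For the purposes of this trial the following events will not require reporting as SAEs". Two items on it matter here. One is "supportive care for disease treatment related toxicities (e.g. neutropenic sepsis, vomiting for cancer participants) (unless there is concern this has been exacerbated by vaccination". The other is "Disease progression (unless there is concern this has been exacerbated by vaccination". Neither exception mentions AZD7442, IMPs or trial treatment in general.

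Elsewhere the protocol treats AZD7442 and the two vaccines as distinct IMPs: in Section 11, in the dosing schedule of Section 11.1, in Table 8 (causality) and in Table 10 (reference safety information). Table 7 defines a serious adverse reaction by a reasonable possibility of relation to the IMP. Sections 14.5.1 and 14.5.2 ask for serious adverse reactions to be reported until the end of follow-up.

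**The concern.** The exception names one class of IMP and leaves out the other. An investigator who suspects that AZD7442 contributed to an admission for progression or treatment toxicity finds no exception in Section 14.2 that covers the case. With the same suspicion about the booster, the event becomes reportable.

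Every cohort is defined by serious disease or its treatment (Section 8.1), so these are foreseeable reasons for admission. Section 4.6.4 says that no clinical study had evaluated AZD7442 combined with booster vaccination, and that the earlier pre-exposure trial included only a small highly immunosuppressed subset. Suspected worsening of underlying disease is thus information that the co-primary safety objective needs. An admission with no SAE form would be missing from that outcome, and the protocol gives it no clear route to causality or expectedness review.

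**Working it through.** No stated figure has to be reproduced. The check is a comparison of provisions, plus one piece of timing arithmetic.

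**1. Can vaccination be read to include AZD7442?** No. The lay summary (Section 3.2) contrasts AZD7442 with vaccinations, and Sections 11, 11.1, 14.3 and 14.4 list them separately.

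**2. Does another rule restore the duty to report?**

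| Provision | Effect on an admission for progression or treatment toxicity suspected of being worsened by AZD7442 |
|---|---|
| Section 14, opening | General SAE duty, but subject to 14.2. The closing sentence on IMP-related SAEs can attach to the duty or to the exception. |
| Section 14.2 | Reporting as an SAE not required, because the concern is not about vaccination. |
| Table 7 | Meets the definition of a serious adverse reaction if a reasonable possibility of relation is accepted. |
| Section 14.3 | Causality assessed for every IMP, on each SAE. |
| Section 14.4 | Expectedness assessed on each serious adverse reaction. |
| Section 14.5.1 | SAE form for events requiring immediate reporting, which leads back to 14.2. Also asks for serious adverse reactions to be reported to the end of follow-up. |
| Section 14.5.2 | Same follow-up rule for the trials unit. |

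The serious-reaction sentences in 14.5.1 and 14.5.2 point towards reporting. They are written as a time window, however, and do not say that they override 14.2. The two sets of instructions conflict, and the more specific one says that reporting is not required.

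**3. When can the trial vaccine trigger the exception?** Inputs: AZD7442 on Day 0; booster on Day 28, plus or minus 3 days (Section 13.1); all-cause SAE reporting to 28 days after the last IMP dose (Section 14.5.1).

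- Window after AZD7442 = booster day + 28. Nominally 28 + 28 = 56 days.
- Share before the booster = booster day / (booster day + 28). Nominally 28/56 = 50%. Early booster: 25/53 = 47%. Late booster: 31/59 = 53%.

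In that first part the trial booster has not been given and cannot be the reason for concern. A standard-of-care booster may have been given at least 28 days before AZD7442 (Section 9.1), so the exception is not impossible to meet, but the trial vaccine cannot meet it. These percentages are shares of calendar time. They say nothing about how many admissions occur or how many would be suspected of involving AZD7442.

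**The case against.** The case on the other side has five parts.

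- **The wording removes a duty and does not forbid reporting.** This stands. A reader might infer that sites are told not to report such events. The text does not say so.
- **A suspected reaction to AZD7442 is a serious adverse reaction, which Sections 14.5.1 and 14.5.2 want reported.** This stands in part. A reader might infer that SUSAR assessment is blocked. The documents do not support that, since a site following the serious-reaction rule would report the event. They do leave the site to choose between two rules.
- **The scope is limited.** This stands. The exemptions sit under a heading about hospitalisations, so death, life-threatening events and the other Table 7 criteria are not clearly exempted. The adverse events of special interest in 14.2 (grade 3 or higher hypersensitivity and injection site reactions, cardiac and thrombotic events, serious SARS-CoV-2 infection up to 28 days after the booster) remain reportable within 24 hours.
- **Toxicity is also recorded at Days 0, 14, 28 and 56, and Section 16.1.6 analyses adverse events as well as SAEs.** True, but toxicity records do not supply the SAE-based co-primary outcome.
- **A wording change comes late.** Section 13.1.1 says recruitment was paused at the beginning of April 2023, and this version is dated 09/05/2023. If nobody was dosed after 1 April, the latest booster day (31 days later) would be 2 May, so the period before the booster was already over. This stands, and it is why the fix includes a look back.

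A reader might also extend the point to the sentence in 14.2 that counts a pre-existing condition only "if the condition worsens by at least one CTCAE grade". That threshold applies equally to every IMP and reads as a deliberate choice. It is a debatable trade-off and not part of this finding.

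**Conclusion.** The rule is wrong as written. Two exemptions in Section 14.2 can be lifted for concern about the booster but not for concern about AZD7442, although both are IMPs and the co-primary safety objective covers both. The supported consequence is possible under-reporting of hospitalisations suspected of being worsened by AZD7442, with a risk that some do not reach causality and expectedness review.

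The size cannot be derived, because the protocol gives no rate for such admissions or for suspicion of AZD7442. The period of about 50% must not be read as half the events lost. Nor is this a bias between randomised arms: all participants receive AZD7442, so the effect would be an undercount in a single-treatment safety summary. The conclusion assumes that sites apply 14.2 literally where it conflicts with 14.5. Sites that gave the serious-reaction rule precedence would lose nothing.

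**What to change.** 1. In both Section 14.2 bullets, extend the exception from vaccination to any IMP, naming AZD7442 and the booster vaccine.
2. State in Sections 14 and 14.5.1 that a suspected serious adverse reaction to any IMP is reportable whatever the 14.2 exemptions say, and make clear what the closing sentence on IMP-related SAEs in the opening of Section 14 attaches to.
3. Because recruitment was paused in April 2023, ask sites to review hospitalisations already treated as exempt for suspected involvement of AZD7442, and to submit SAE forms where it is found.

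The cost is a few wording edits, a site notification, a one-off check of exempted admissions and some additional SAE forms. The exemptions for admissions in which no IMP is suspected stay in place.
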